9.3.3. Covariates

Covariates to be evaluated include the following, some of which will be used to adjust or stratify the cohort during the analytic modeling:

- Region of residence within US [as defined by either Department of Health and Human Services (11 regions) or Census Bureau (4 regions)]
- Calendar year-month of vaccination or preventive care visit
- Age in years at vaccination or preventive care visit (aggregated into age groups: 65-69, 70-74, 75-79, 80-84, 85+)
- Sex (binary as male/female)
- Race and ethnicity (e.g., white, black, Asian, Hispanic, North American Native, other)
- Concomitant vaccination (e.g., influenza, pneumococcal, etc.)
- Certain immunocompromising conditions (e.g., transplant, cancer, autoimmune/inflammatory condition, etc.)
- Certain other co-morbidities (e.g., diabetes mellitus, chronic obstructive pulmonary disease, congestive heart failure, etc.)

9.3.4. Potential confounding variables and effect modifiers

A confounder is defined as any variable that is associated with both the exposure and the study HOI. Since a confounder cannot be on the causal pathway from exposure to the outcome, all confounders will be captured in the 365 days preceding the index date, i.e., RZV Dose 1 and Dose 2 vaccination date and the RZV unvaccinated comparator preventive care visit for the cohort design. All confounders identified using Medicare enrollment and medical or prescription claims data will be used for covariate adjustment in multivariable models. Propensity score methods will be considered for confounding adjustment, depending on identified imbalances in the observed covariates between the exposed and comparator groups. Confounding variables defined by health care services and comorbidities will be identified using a combination of ICD-10, CPT and HCPCS codes.

- **Demographic variables** will include age, sex, and race and ethnicity (i.e., white, black, Asian, Hispanic, North American Native, and other/unknown based on the US government categories)
- **Healthcare service variables** will include admissions to skilled nursing facilities (SNFs), number of hospitalizations, number of ED visits and Durable Medical Equipment (DME) use. These will be considered to control for potential imbalances between RZV vaccinees and RZV unvaccinated comparators in health impairment requiring more intensive services. The place of service and revenue code on the claim are used to designate the type of service setting.
- **Preventive care services** will include receipt of age-recommended vaccine (e.g., influenza, pneumococcal, and tetanus, diphtheria, pertussis). These will be

considered to control for potential healthy adherer bias that could result in imbalances in healthcare services and prior health seeking behavior patterns between RZV vaccinees and RZV unvaccinated comparators. Table 2 lists the preventive care services. Since mammography, bone mineral density, and colorectal screening are criteria for the unvaccinated comparator selection, these are not included as confounders in the analysis.

- **Medical comorbidities specific to PMR/GCA**. Potential risk factors specific to these conditions may include:
 - Age, which is found to be the strongest risk factor;¹⁹
 - Female sex is found to be a risk factor;¹⁹
 - Race/ethnicity as a significantly lower incidence is reported in African, Asian, Latinos;¹⁹
 - Gout has been associated in a few studies (from same group using CMS data);^{20,21}
 - Prior hematologic malignancy has conflicting results on the association, but has been shown in some studies;²²
 - Case reports/series with use of checkpoint inhibitors show development of PMR or PMR-like syndrome;²³
 - Immunocompromising conditions, given that PMR is an immune-mediated disorder, potentially imbalance in T-regulatory lymphocytes and proinflammatory T-helper 17 cells.
- **Medical comorbidities specific to ION**. Risk factors specific to ION include:²⁴⁻²⁸
 - Arteritic ION is significantly less common than non-arteritic and is strongly associated with GCA, thus we will consider similar risk factors/potential confounders.
 - Non-arteritic ION Anterior Ischemic Optic Neuropathy has reported associations with obstructive sleep apnea, vasculopathic/ prothrombotic conditions (e.g., diabetes, hypertension, spinal and cardiac surgery, some medications (amiodarone, phosphodiesterase type 5 inhibitors).
- **General medical comorbidities**. Other comorbidities or chronic conditions may be important to address confounding by indication, e.g., relatively common conditions that are indicative of functional status or illness severity.
 - Diabetes mellitus
 - Chronic kidney disease
 - Chronic lung disease chronic obstructive pulmonary disease and chronic bronchiectasis
 - Congestive heart failure
 - Ischemic heart disease
 - Dementia Alzheimer's Disease and Related Disorders or Senile Dementia

- Chronic liver disease cirrhosis and other liver conditions except hepatitis
- Stroke/Transient Ischemic Attack
- **Immunocompromised conditions**. This includes solid organ transplant, hematopoietic cell transplant, hematologic or solid malignancy with recent receipt of chemotherapy, autoimmune/inflammatory condition *or* on an immunosuppressive regimen, and human immunodeficiency virus infection.

9.4. Data sources

9.4.1. Description of the databases (Amended 15 July 2022)

CMS CCW Medicare data is a secondary administrative database of all paid claims for fee-for-service billable healthcare services in inpatient and outpatient settings, SNF, hospice, home health services, and for the provision of DME and prescription drugs for older and disabled US citizens. The claims data are available in six different datasets and a unique identification (ID) is used to link an individual across all data sets. Annex 1 provides a detailed description of the data sets and the variables within each dataset.

Master Beneficiary Summary File (MBSF): The information in this dataset relevant to this study includes beneficiary enrollment *each calendar month* in Medicare Parts A, B, and D. This file will be used to obtain information on the baseline study variables, including original and current enrollment reason, eligibility, and demographic characteristics.

Inpatient Claim File: This dataset contains fee-for-service claims submitted by inpatient hospital providers for reimbursement of facility costs, including hospitalizations and ED visits. Up to 25 diagnosis fields, including the admission diagnosis as well as a principal diagnosis, are available on each claim. CPT codes for services rendered are available on each claim.

Outpatient Claim File: This dataset contains fee-for-service claims submitted by *institutional outpatient providers*. Institutional outpatient providers include hospital outpatient departments, rural health clinics, renal dialysis facilities, outpatient rehabilitation facilities, comprehensive outpatient rehabilitation facilities, Federally Qualified Health Centers and community mental health centers. The outpatient files contain up to 25 diagnosis fields as well as CPT codes.

Carrier File: This dataset includes fee-for-service claims submitted by *professional providers*, including physicians, physician assistants, clinical social workers, nurse practitioners and by *organizational providers*, including freestanding facilities (i.e., independent clinical laboratories), ambulance providers, freestanding ambulatory surgical centers and freestanding radiology centers. The Carrier files contain up to 12 diagnosis fields as well as CPT codes.

SNF Claim File: This dataset includes fee-for-service claims for paid services that are submitted by SNF *institutional facility providers*.

PDE File: This dataset includes all medications filled at an *outpatient pharmacy* that have been submitted by the prescription drug plan. The NDC variable will be used in this study to identify all medications dispensed during the baseline and follow-up period.

The MBSF will be used primarily to select the study population and determine eligibility for this study. The inpatient, outpatient, carrier and SNF files will be used to ascertain the HOIs and the confounding variables. The PDE file will be used to ascertain RZV exposure.

9.4.2. Quality of the data

Quality of the ICD Codes for Identifying HOIs: The chronic medical condition variables were developed using algorithms based on ICD-9-CM diagnoses codes, Medicare Severity Diagnosis Related Group codes, or procedure codes. CMS has confirmed the consistency of the prevalence of the chronic conditions between the ICD-9 and ICD-10 codes. The link to the document is found here: https://www2.ccwdata.org/web/guest/ccw-medicare-datra-white-papers. All of the algorithms used to identify CCW chronic conditions from the claims data were updated for the conversion from ICD-9 to ICD-10. However, the validation statistics for these algorithms are not reported in the CCW white paper. Specifications for the algorithms are located under the 'Conditions Categories' tab at www.ccwdata.org. With regards to the HOIs in this study, gout (see Sentinel report) has demonstrated consistent prevalence during the period of transition from ICD-9 to ICD-10.

Completeness of the CMS CCW Medicare Claims for Assessment of Study Outcomes: The claims from each of the databases are over 99% complete by 12 months post-service date. This will reduce the likelihood of missing information as all data measured for this study will have a minimum of a one-year lag period.

This study uses de-identified Medicare data curated for research; investigators cannot access medical charts for case adjudication. Case identification will be limited to use of an algorithm that combines medical billing diagnosis code, procedure and/or drug codes.

9.4.3. Number of years and duration of data availability

For this study, five years of CCW Medicare data will be purchased: 2017 through 2021. This is necessary to ensure an adequate sample size for the primary HOIs (see Section 9.5 for a detailed description of the sample size). The span of five years (2017 through 2021) will ensure claims data are available for 365 days preceding the HOI (in the SCRI design) and the index date (in the cohort design) and throughout the duration of the study follow up for all of the Dose 1 and Dose 2 analyses. All individuals will be followed longitudinally throughout the study.

CCW Medicare data are available for request in December for the prior year's claims (e.g., the 2018 data should be available for request in December 2019).

9.4.4. Rationale for selecting the database and advantages

Rationale for Selecting the Database: Several factors support the rationale for using the CMS CCW Medicare data.

- It is the largest comprehensive dataset of healthcare service utilization of US adults age 65 and older.
- Data linkage across different data sets permits evaluation across the continuum of healthcare settings and services.

Advantages of the CMS CCW Medicare Data: The CMS CCW Medicare data offers many strengths for a vaccine safety study using observational data. The relevant strengths of CCW Medicare for this study include:

- There is continuity of medical and prescription claims data. Once enrolled, most beneficiaries remain enrolled in Medicare for the rest of their lives because Medicare is the only entitlement health insurance coverage for older adults in the US. The exception is adults who enroll in Part C, and all of their data are missing because it is not captured in the CMS CCW fee-for-service data. The feasibility assessment revealed that, 54% of the Medicare beneficiaries had continuous enrollment in Parts A, B, and D for at least one-year preceding the first occurrence of a claim with a diagnosis corresponding the one of the HOIs in this study. Most Medicare beneficiaries (56%) were continuously enrolled in Parts A, B, and D for at least oneyear after the first occurrence of a claim with a diagnosis corresponding to one of the HOIs in this study. Approximately 20% were continuously enrolled in Parts A, B, and D for five or more years. This will ensure sufficient data for the baseline and follow up assessments in this study with minimal loss to follow-up.
- 2. Comprehensive data that are linkable across service settings. The data will include medical and prescription encounter data from inpatient, institutional, outpatient physician, outpatient hospital, and outpatient pharmacies that are linked via a beneficiary identification number. This permits assessment of the study outcomes in relation to the timing of a medication exposure, including vaccines. Key variables include those related to diagnoses, procedures, and place of service.
- 3. Large population. The Medicare population is large and will permit detection of rare outcomes, as some HOI in this study like GBS, GCA and ION are rare.
- 4. Representation of geographic diversity of the US, since the data represent all Medicare enrollees across all states. The data provide geographic diversity within the context of the US.

9.5. Study size

9.5.1. Projected study size

CMS CCW Medicare claims data will be obtained for up to 20 million Medicare beneficiaries. This will include all RZV vaccinees in 2018 through 2020 in addition to a random sample of Medicare beneficiaries who did not receive RZV and had a preventive care visit. The estimated sample size for the SCRI design with vaccinees (Table 4) and the cohort design with vaccinees and the unvaccinated comparators (Table 4) needed to detect the specified relative risk with 80% power is attainable.

9.5.2. Sample size considerations

SCRI design sample size estimates

For the SCRI design, the required number of events was calculated based on the method for self-controlled case series studies²⁹. The sample size estimates shown in Table 4 indicate that 1 000 000 individuals are needed to detect a relative risk of at least 4.0 for GBS and 70 000 individuals are needed to detect a relative risk of 2.0 for gout. The sample size calculation only takes into consideration the control window because the risk of GBS or gout in the control window would reflect the background risk. Due to the dose spacing and the possibility of Dose 1 control window overlapping the risk window for Dose 2, the full 42-day control window for Dose 1 may not be observed, we expect this to occur in about 50% of 2 dose vaccine recipients (based on internal GSK data from 2018-2019 regarding timing of Dose 2 receipt in the US). Hence the average length of the control window observed would be about 36 days.

Table 4SCRI design sample size estimates for GBS and gout with 80%
statistical power under a two-sided type 1 error (alpha) of 0.05

Outcome	IR	CW (days)	Scalar of Risk Window	No. of cases expected per 100 000 CWs ^a	RR	Total events needed	*No. of cases expected in CW	No. of CWs (aka vaccinations) needed/100 000 ^b	**No. vaccinations needed	***No. of vaccinated people needed
	2/100 000				3	30	8	41	4,100,000	2,050,000
GBS	2/100 000 PY	36	0.098563	0.197125	4	20	4	20	2,000,000	1,000,000
	200/100 000	0			2	68	23	140	140,000	70,000
Gout	200/100 000 PY	30	0.082136	8.706365503	2.5	40	11	67	67,000	33,500

IR: Incidence rate; RR: Relative risk; CW: Control window

^a Assuming no risk from vaccination exists in CW

^b vaccinations are synonymous with post-vaccination control windows

*Total events needed were calculated using the method described by Musonda et al 29.

** Expected vaccinations were obtained assuming the control window was truly not a period od=f increased risk

*** Approximate numbers, assuming that individuals receive 2 doses

In order to use the control window (assumed to be free of risk due to vaccination) to project the number of vaccinations needed, we scaled the background risk to the length of the control window, i.e., multiplied the respective background rate by 36/365.25 for GBS and by 30/365.25 for gout.

We then calculated the number of cases we would need in the control window for each relative risk scenario, given the minimum total number of events needed in risk and control windows combined.

For example, for a true relative risk of 2, a total of 71 cases are needed to achieve 80% power to see an association. We would expect about 47 of the 71 cases to be in the risk window and 24 to be in the control window.

To generalize to other relative risk scenarios, the number of cases in the control window out of the total events needed is [total events needed/(RR+1)]. The expected numbers in the control window (vaccinations) needed is simply the ratio of the number of cases in the control window (i.e., the number expected on the basis of the true relative risk and the total number of events needed in risk and control windows combined) and the background rate scaled to the control window length.

Cohort design sample size estimates:

For the cohort design, the sample size was estimated using Poisson Regression in the Power Analysis and Sample Size software (NCCS Statistical Software, 2013, version 12.0.2). The analysis performed for the PMR and GCA sample size estimates was based on a 183-day risk period with a cohort ratio of 1:4 exposed to unvaccinated preventive care visit comparator.

The sample size estimates shown in Table 5 indicate that a total sample of 438 239 individuals is needed to detect a relative risk of 2.0 for PMR and a total sample of 723 362 individuals are needed to detect a relative risk of 3.0 for GCA. The study is powered for the primary outcomes of PMR and GCA.

Table 5Sample sizes with cohort design for PMR and GCA with 80%
statistical power under a two-sided type I error (alpha) of 0.05,
Cohort 1:4 ratio, and 6 months follow up

Outcome	RR	Baseline	Total Cohort	Vaccinated	Control Population,
Outcome		Response	Sample Size, N	Population, N	N
PMR	2		438,239	87,648	350,591
	2.5	0.000405	242,212	48,442	193,770
	3	0.000405	164,320	32,864	131,456
	3.5		123,991	24,799	99,192
	2		1,929,204	385,841	1,543,363
	2.5		1,066,257	213,252	853,005
GCA	3	0.000092	723,362	144,673	578,689
	3.5		545,828	109,166	436,682
	4		439,133	87,827	351,306

The estimated sample sizes for the SCRI design with vaccinees (Table 4) and the cohort design with vaccinees and the unvaccinated comparators (Table 5) needed to detect the specified relative risks (≥ 4 for GBS, ≥ 2 for gout, ≥ 2 for PMR, and ≥ 3 for GCA) with 80% power is attainable.

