9.3.2. Outcome identification algorithms

The primary HOIs are GBS, gout, PMR, and GCA. Secondary HOIs are SVT and ION. Table 3 describes the case definition algorithm for the primary and secondary HOIs, which also details the sensitivity analyses where validated outcome identification algorithms are not available in the literature for reference.

- All algorithms use medical claims from the inpatient, outpatient or carrier claim files and are based on the ICD-10 codes.
- An inpatient claim is defined as a claim generated from an admission to a hospital.
- An ED (Emergency Department) visit is defined as a claim generated from a visit to an urgent care unit within a hospital, but it is not a hospital admission.
- An outpatient claim is defined as a claim generated by a visit to a provider in an ambulatory practice setting, e.g., physician office, health clinic.
- For algorithms that require ≥ 2 claims, the date of the first claim will define the first occurrence of the HOI. The two claims must occur within the designated follow-up interval.
- For the SCRI design, new onset of the HOI, i.e., incident case, is determined based on the first occurrence and no record of the HOI in the preceding 365 days.
- For the cohort design, new onset of the HOI, i.e., incident case, is determined based on the first occurrence after the index date (i.e., RZV vaccination or the preventive care visit date for RZV unvaccinated comparators) and no record of the HOI in the 365 days preceding the index date (i.e., baseline period).
- For GBS, the earliest onset date is the hospitalization date for claims in the inpatient setting or the earlier GBS claim when the diagnosis occurs in any setting followed by an inpatient claim within 7 days.

Table 3HOI case identification algorithms

1	2	3	4	5	6	7	8	9	10
Study Outcome (Study design)	ICD-10 code(s) for case ascertainment	Validation Statistics	Other requirements ^c	Setting for case ascertainment	Risk Interval	Look-back period & settings to determine incidence	What to look back for	What to look back from	Sensitivity Analysis
GBS (SCRI)	G61.0	PPV: 50% (Inpatient visit) ¹⁴	None	Inpatient primary position OR Diagnosis in any setting followed by an inpatient claim within 7 days	Days 1-42	1 year; inpatient; primary position only	Same as in Col.2	HOI	N/A

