Gout (SCRI)	M10.x, M1A.x (chronic gout)	PPV: 61% (≥ 2 visits associated with the diagnosis) ¹⁵	At least one gout- specific oral medication (allopurinol, colchicine, probenecid, febuxostat) prescribed within 3 months after the first date of the diagnosis.	≥2 outpatient claims within the follow-up windowa OR ≥1 inpatient claim	Days 1-30	1 year; diagnosis code –all settings ^b OR At least one gout- specific oral medication (allopurinol, colchicine, probenecid, febuxostat);	Same as in Col. 2 OR Col. 4	HOI	-Exclude chronic and secondary gout codes. -Examine frequency distribution of ICD-10 codes and consider low- frequency codes such as codes for chronic gout (M1A*), lead- induced gout (M10.1*, drug-induced gout (M10.2*), and gout due to renal impairment (M10.3*) (note: this exclusion of gout codes does not apply in assessing prevalent gout) ^d

209696 (EPI-ZOSTER-032 VS US DB) Protocol Amendment 3 Final

1	2	3	4	5	6	7	8	9	10
Study Outcome (Study design)	ICD-10 code(s) for case ascertainment	Validation Statistics	Other requirements ^c	Setting for case ascertainment	Risk Interval	Look-back period & settings to determine incidence	What to look back for	What to look back from	Sensitivity Analysis
PMR (Cohort)	M35.3 – PMR M31.5 – GCA w/ PMR	Sensitivity: 99.5% Specificity: 92.2% ¹⁶ (based on the 3 methods used by Bernatsky: diagnosis in inpatient or outpatient, or a visit by a rheumatologist/ internist)	2 oral glucocorticoids (cortisone, dexamethasone, hydrocortisone, methylprednisolone, prednisolone, prednisone) prescriptions; The first dispensing within 6 months of PMR diagnosis and the second dispensing date within 6 months after the first dispensing.	≥2 outpatient claims within the follow up window a OR ≥1 inpatient claim	Days 1-183	1 year; all settings⁵	Same as in Col. 2	Exposure	N/A
GCA (Cohort)	M31.6 (GCA), M31.5 (GCA with PMR), M31.9 (necrotizing vasculopathy unspecified)	Not available	2 oral glucocorticoids (cortisone, dexamethasone, hydrocortisone, methylprednisolone, prednisolone, prednisone). The first dispensing within 6 months of GCA diagnosis and the second dispensing date within 6 months after the first dispensing.	≥2 outpatient claims within the follow up windowª OR ≥1 inpatient claim	Days 1-183	1 year; all settings⁵	Same as in Col. 2	Exposure	-Use the primary algorithm based on the GCA diagnosis code and steroid prescription but ADD a requirement for a temporal artery biopsy at the time of diagnosis, as determined by a CPT code=37609

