Case ascertainment. It will not be possible to conduct a chart review to validate HOIs. Case-finding algorithms using administrative data are rarely sensitive and specific. The algorithms used in this study are found to have high positive predictive value in published case validation studies and we consulted with experts.

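### The 80% power stated for GBS and gout makes no allowance for false-positive cases, although Table 3 lists PPVs of 50% and 61%; one cell and one column unit in the gout row of Table 4 are also wrong

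*Combined protocol and SAP*

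**What the plan says.** - **Power.** The Abstract claims at least 80% power if the true relative risk (RR) is 4 or more for GBS and 2 or more for gout. Section 9.5.2 says that "1 000 000 individuals are needed to detect a relative risk of at least 4.0 for GBS", and 70 000 for an RR of 2 in gout, where "the required number of events was calculated based on the method for self-controlled case series studies". Table 4 gives 20 total events for GBS and 68 for gout. Section 9.7.1.1 makes testing conditional on at least 20 recorded GBS cases and 68 recorded gout cases, and attaches the 80% power to those conditions.
- **Case definitions.** Table 3 (section 9.3.2) gives "PPV: 50% (Inpatient visit") for GBS and "PPV: 61% (≥ 2 visits associated with the diagnosis") for gout. It gives sensitivity and specificity for PMR, sensitivity only for SVT, and nothing for GCA or ION. Sections 9.4.2 and 9.9 say that charts cannot be reviewed.
- **Limitations.** Section 9.9 states: "The algorithms used in this study are found to have high positive predictive value in published case validation studies".
- **Gout row of Table 4.** The text says that the sponsor "multiplied the respective background rate by 36/365.25 for GBS and by 30/365.25 for gout". The row lists a rate of 200/100 000 person-years (PY), a scalar of 0.082136 and 8.706 expected cases per 100 000 control windows.

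**The concern.** In a self-controlled design, false-positive cases whose timing has nothing to do with vaccination fall in the risk and control windows in proportion to window length, and so pull the observed rate ratio towards 1. The power claim is worded for the true RR, but the event counts are those needed if that RR were observed undiluted. With listed PPVs of 50% and 61% the gap is large.

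This matters most for GBS, the rarest SCRI outcome and the one with a prior surveillance signal. A non-significant GBS result would be read against a stated 80% power that may not apply. Section 9.9 adds to this by describing the PPVs as high when the only two listed are 50% and 61%.

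Separately, the 8.706 cell does not follow from the rate and scalar printed beside it, which leaves open which gout rate was intended.

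**Working it through.** **Inputs.** Two-sided alpha 0.05, 80% power, rates 2 and 200 per 100 000 PY, control windows of 36 days (GBS average) and 30 days (gout), two doses per person (all section 9.5.2 and Table 4). Risk windows of 42 and 30 days (Table 1). PPVs from Table 3.

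**1. Reproducing the plan.** With r the risk-window share of observed time and p = r·RR/(r·RR + 1 − r), the signed-root likelihood-ratio formula for case series is n = (1.96 + 0.842·√B)²/A, where A = 2[p·ln RR − ln(r·RR + 1 − r)] and B = (ln RR)²·p(1 − p)/A.
- GBS, RR 4: n = 19.1 at r = 0.5 and 20.2 at r = 42/78 (plan: 20). Control-window cases 20/(4 + 1) = 4. Expected per 100 000 windows: 2 × 36/365.25 = 0.1971. Vaccinations: 4/0.1971 × 100 000 ≈ 2.03 million, or about 1.01 million people (plan: 1 000 000).
- Gout, RR 2: n = 68.1 at r = 0.5 (plan: 68). Control-window cases 68/3 = 22.7, rounded to 23. Expected per 100 000 windows: 200 × 30/365.25 = 16.43. Vaccinations: 23/16.43 × 100 000 ≈ 140 000, or 70 000 people (plan: the same).

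Both headline sizes reproduce, and neither contains a misclassification term.

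**2. The gout row.** The printed 8.706 divided by 0.082136 implies 106/100 000 PY, not 200. The 140 and 67 in the column headed as needed/100 000 should be 1.40 and 0.67; they are in thousands. The GBS rows use the header unit correctly.

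**3. Dilution.** If false positives are spread evenly over time, observed RR = 1 + PPV × (RR − 1), with the PPV taken as that of background cases.
- GBS: 1 + 0.50 × 3 = 2.5. Events needed: 40.1 (r = 0.5) to 41.9 (r = 42/78).
- Gout: 1 + 0.61 × 1 = 1.61. Events needed: 141.

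**4. Power at the recorded-case thresholds.** With 20 GBS cases and RR 2.5, exact conditional power is 39% (r = 42/78) to 47% (r = 0.5). With 68 gout cases and RR 1.61 it is 45%. The plan's own formula gives about 47–50% and 49%.

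**5. Power at the stated sizes.** Exact two-sided conditional binomial test, averaged over Poisson totals; windows 42:36 (GBS) and 30:30 (gout).
- GBS, 1 000 000 people, PPV 50%. If 2/100 000 is a coded rate: control 2 000 000 × 2/100 000 × 36/365.25 = 3.94, risk 2 000 000 × 2/100 000 × 42/365.25 × 2.5 = 11.5, total 15.4; power 29%. If it is a true-case rate, the coded rate is 2/0.50 = 4 and the total 30.9; power 59%. With perfect PPV: 76%.
- Gout, 70 000 people, PPV 61%. Coded rate: 23.0 + 37.0 = 60.0 cases; power 40%. True-case rate (200/0.61 = 328 coded): 37.7 + 60.7 = 98.4 cases; power 61%. With perfect PPV: 77%.

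**6. Power at the expected size.** Section 9.2.2 expects a little more than 2 million eligible vaccinees. At 2 million, all with two doses, gout yields 60.0 × 2 000 000/70 000 ≈ 1 715 coded cases against 141 needed. For GBS at true RR 4, the method of step 5 gives:

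| PPV | Observed RR | Power, coded rate | Power, true-case rate |
|---|---|---|---|
| 50% | 2.5 | 59% | 90% |
| 70% | 3.1 | 84% | 95% |
| 80% | 3.4 | 91% | 96% |
| 100% | 4.0 | 98% | 98% |

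**The case against.** - **The PPVs are borrowed.** The 50% is for an inpatient visit, from a study whose title concerns adolescents; this study requires primary position, or a diagnosis followed by an inpatient claim within 7 days, in people aged 65 and over. The 61% is for two or more visits; this study also requires a gout drug. The applicable PPVs are unknown and may be higher. This stands. It argues for a range, not for an implicit 100%: even at an assumed GBS PPV of 80%, exact power at 1 000 000 people on the coded rate is about 60%.
- **The stated sizes are minimums.** At the expected 2 million, gout has no practical power problem. This stands. For GBS it holds only in part, and the 2 million figures assume that everyone receives two doses.
- **Not all of the shortfall is due to PPV.** An exact test averaged over random totals gives about 76–77% even with perfect PPV. By the plan's own type of formula, the figures at the stated sizes are 36–64% for GBS and 44–65% for gout. The conclusion is the same.
- **The limits are partly acknowledged.** Section 9.9 concedes that claims algorithms are rarely sensitive and specific, and the confidence intervals will show the precision achieved. Neither corrects the power statement, and an interval around a diluted ratio is still centred on the diluted value.
- **The gout sample size.** A reader might infer from the 8.706 cell that 70 000 is wrong and should be about 132 000 (23/8.706 × 100 000 = 264 000 vaccinations). The documents do not support that: the table states 200/100 000 PY, the text confirms the 30/365.25 scaling, and 68 events, 140 000 vaccinations and 70 000 people all follow.

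**Conclusion.** The power statement is wrong as written for the true RR: it holds only for the RR as defined by the claims algorithms. At the listed PPVs the required cases roughly double (20 to 40–42 for GBS, 68 to 141 for gout), and exact power at the stated sizes is 29–59% and 40–61%. This rests on three assumptions: false positives unrelated to vaccination, the Table 3 PPVs applying to background cases, and a background rate that is either coded or true-case, which the plan does not say.

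It would be too strong to conclude that the study as expected is underpowered. Gout is not. GBS power at 2 million two-dose vaccinees falls below 80% only if the rate is a coded rate and the PPV is below roughly 70%. The description of the PPVs as high conflicts with Table 3. The errors in the gout row are confined to one cell and one column unit.

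**What to change.** 1. In the Abstract and sections 9.5.2 and 9.7.1.1, state that the 80% power and the thresholds of 20 and 68 cases refer to the algorithm-defined RR.
2. Say whether the rates of 2 and 200 per 100 000 PY are coded or true-case rates.
3. Tabulate power, or the detectable true RR, for GBS and gout over a PPV range (for example 50–100%) at the expected number of vaccinees.
4. Replace the section 9.9 sentence with the Table 3 values, noting that they come from definitions differing from the study algorithms and that no PPV is listed for the other outcomes.
5. In Table 4, correct 8.706 to 16.43, or confirm the intended gout rate and recompute the row; correct the unit of the 140 and 67.

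Optionally, report a PPV-corrected rate ratio, (IRR − (1 − PPV))/PPV, over a PPV range as a sensitivity analysis. Its assumption of evenly spread false positives must be stated, and it turns negative when the IRR is below 1 − PPV.

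The cost is text and one table, with no new data. The downside is that the stated power becomes less favourable.
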